9.1.7. Adverse Events Leading to Treatment Discontinuation

TEAEs with a study treatment action taken of ‘Drug Withdrawn’ will be considered as TEAEs leading to treatment discontinuation and will be summarized by SOC and PT.

A by-patient listing will also be provided for all adverse events leading to treatment discontinuation and ordered by site.

9.1.8. Adverse Events Leading to Study Discontinuation

TEAEs leading to study discontinuation as per recorded on the eCRF ‘Adverse Event’ page will be summarized by SOC and PT.

A by-patient listing will also be provided for all adverse events leading to study discontinuation and ordered by site.

9.1.9. Adverse Events Leading to Death

A by-patient listing will also be provided for all adverse events leading to death and ordered by site.

9.1.10. Adverse Drug Reactions (ADRs)

ADRs will be summarize by SOC, PT and by severity. Serious ADRs will be summarized by SOC and PT.

A by-subject listing will also be provided for all ADRs and ordered by site.

9.2. Pregnancy Test

For women of child-bearing potential, pregnancy test will be performed at screening, Baseline, and Visit 4/Week 4 (EOT) Visits.

Pregnancy test results will be presented in a by-patient listing and ordered by site.

9.3. Treatment Discontinuation due to Tolerability

Number and percentage of patients discontinued study treatment due to tolerability will be summarized as per recorded in the eCRF End of Treatment page.

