	
average in the Study Eye only at selected sites that have the required equipment (Oculus keratograph 5M) [Time Frame: at weeks 4 (V4) and 8 (V5)]
 
 • Mean change from baseline in response to CCI [Time Frame: week 4 (V4)] • Mean change from baseline in total corneal fluorescein staining (NEI scale) in the Study Eye as assessed by the investigator [Time Frame: at week 8 (V5)] • Mean change from baseline in total conjunctival lissamine green staining (NEI scale) in Study Eye as assessed by the investigator [Time Frame: at week 8 (V5)] • Validate an Italian version of the CCI [Time Frame: at baseline, week 4 (V4)]
Safety Endpoint	
 • Safety will be monitored by the incidence and frequency of Treatment-Emergent Adverse Events (TEAEs) assessed throughout the study including Run-In period. • Mean change from baseline in corneal endothelial cell density in both eyes performed at sites that have a specular microscope [Time Frame: at week 8 (V5)] • Change from baseline in the proportion of patients with vitritis, retinal or vitreal hemorrhages, increase in cup-to-disc ratio, retinal or posterior vitreal detachment, retinal tears, or maculopathy on dilated fundus exam (DFE) in both eyes [Time Frame: at week 8 (V5)] • Mean change from baseline in bulbar conjunctival redness in both eyes (VBR 10 score) [Time Frame: at weeks 4 (V4) and 8 (V5)] • Treatment discontinuation rate due to tolerability issues.
Methods, procedure and assessment	
Site staff will conduct the following assessments and activities in the order outlined below during each visit.
 
Visit 1 (Day -12±2): SCREENING
 
 1. Informed Consent/HIPAA (HIPAA only for USA) 2. Demographics, Ocular and Medical History, Previous and Concomitant Ocular and Systemic Medications and Conditions 3. Pregnancy Test 4. SANDE questionnaire 5. Ophthalmic Examinations for each eye: 
 A. Best-Corrected Distance Visual Acuity (BCDVA) by ETDRS

Information	Description

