7 DISCONTINUATION OF TRIAL INTERVENTION AND PARTICIPANT WITHDRAWAL FROM TRIAL

7.1 CRITERIA FOR DISCONTINUATION OF TRIAL INTERVENTION

7.1.1 Criteria for Permanent Discontinuation of Trial Intervention

Treatment discontinuation

Patients with tolerability issues, or worsening of symptoms and/or signs may be discontinued at any time during the study for the following reasons:

- 1) AEs that at Investigator discretion require treatment discontinuation.
- 2) Worsening of the clinical condition that requires treatment discontinuation per physician decision or ocular surgery.
- 3) Violation of study procedures that represent a protocol deviation deemed by the Investigator to require treatment discontinuation.
- 4) Withdrawal of patient's consent for any reason.
- 5) Patient is lost-to-follow-up notwithstanding all efforts to contact him/her (at least three documented attempts by phone and/or email).
- 6) Other (e.g., death, pregnancy, planned operation).

Except for items from #4 to #6 of the list reported above that imply also a study discontinuation, in case one of the events from #1 to #3 occurs, patients will be asked to complete the assessments planned by the protocol regardless the discontinuation of the study treatment and will receive preservative free AT, TID, provided by the Sponsor. In case of more than one reason, the main one will be reported in eCRF.

Study discontinuation

A premature discontinuation will occur when a patient who signed the ICF ceases participation in the study, regardless of circumstances, before the completion of the study protocol procedures.

Patients should be discontinued from the study for one of the following reasons:

- 1) Withdrawal of patient's consent for any reason.
- 2) AEs, protocol deviations and any other condition for which study procedures may compromise the safety and well-being of the patient, as per physician decision.
- 3) Patient is lost-to-follow-up notwithstanding all efforts to contact him/her (at least three documented attempts by phone and/or email).
- 4) Other (e.g., death, pregnancy, planned operation).

In all other situations, including cases where patients should be discontinued from study treatment, all efforts will be made to complete study visits and procedures as per protocol.

Before removal, each case should first be discussed with Dompé.

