
 To evaluate the efficacy of the new formulation of rhNGF ophthalmic solution in improving best corrected visual acuity in DED as compared to vehicle at weeks 4 and 8 	
 Mean change from baseline in BCDVA score [Time Frame: at weeks 4 (V4) and 8 (V5)]
Safety Objectives	Safety Endpoints

 To evaluate safety/tolerability of the new formulation of rhNGF ophthalmic solution 	
 Safety will be monitored by the incidence and frequency of treatment-emergent adverse events (TEAEs) assessed throughout the study including run-in period.

 To evaluate safety of the new formulation of rhNGF ophthalmic solution 	
 Mean change from baseline in corneal endothelial cell density in both eyes [Time Frame: at week 8 (V5)] Change from baseline in the proportion of patients with vitritis, retinal or vitreal

Objectives	Endpoints
	
hemorrhages, increase in cup-to-disc ratio, retinal or posterior vitreal detachment, retinal tears, or maculopathy on dilated fundus exam (DFE) in both eyes [Time Frame: at week 8 (V5)]
 
 Mean change from baseline in bulbar conjunctival redness (VBR 10 score) in both eyes [Time Frame: at weeks 4 (V4) and 8 (V5)]

 To evaluate tolerability of the new formulation of rhNGF ophthalmic solution. 	
 Treatment discontinuation rate due to tolerability will also be evaluated.
CCI	CCI

 CCI 	
 CCI
CCI	

(**) Only in patients with CCI
	

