5.1. Disposition

The number of patients who were screened, and the eligibility criteria met/failed will be summarized based on all screened patients. The number and percentage of screen failure patients will be summarized for each exclusion criteria met and/or inclusion criteria failed.

Disposition of all randomized patients will be summarized by treatment group including:

- Full Analysis Set
- Safety Set
- Per-Protocol Set
- Number of patients who completed the study treatment
- Number of patients who prematurely discontinued the study treatment
 - Number of patients who prematurely discontinued the study treatment but complete the study
 - Number of patients who prematurely discontinued the study treatment and discontinued the study
- Primary reason for treatment discontinuation
- Number of patients who completed the study
- Number of patients who prematurely discontinued the study (early termination)
- Primary reason for study discontinuation.
- Number of patients who were unblinded during the study and the reason (Emergency situation, Other).

Primary reasons for treatment discontinuation collected on the eCRF will be summarized with the following categories separately:

- Adverse Event
- Death
- Lost to Follow-up
- Physician Decision
- Protocol Deviation
- Withdrawal by Patient
- Pregnancy
- Treatment Discontinuation due to Tolerability Issues
- Other

Primary reasons for study discontinuation collected on the eCRF will be summarized with the following categories separately:

- Adverse Event
- Death
- Lost to Follow-up
- Physician Decision
- Protocol Deviation
- Screen Failure
- Study Terminated by Sponsor
- Withdrawal by Patient
- Other

The distribution of the time from randomization to study discontinuation will also be summarized using time-to-event analysis. A log-rank test will be used to compare distributions among the three groups (two IMP groups and the Vehicle group).

Screening data will be listed by patients as collected based on all screened patients (SCR). Disposition data will be listed by patients as collected based on all randomized patients (RND) by site.

Inclusion and exclusion criteria deviations will be presented for all screened patients in a data listing by site.

In addition, total study duration from the screening (date of informed consent) to the last visit of each patient will be summarized.

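### The tolerability-discontinuation endpoint is read from a single main reason on the End of Treatment page, so patients who stop for a drug-related ocular adverse event may be missed

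*SAP*

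**What the plan says.** The Protocol synopsis lists among the safety endpoints "Treatment discontinuation rate due to tolerability issues", and the endpoint table in SAP 3.2 repeats it: "Treatment discontinuation rate due to tolerability will also be evaluated". In that table, and in Protocol Table 3, it is the only endpoint in the row for the stand-alone tolerability objective. TEAE incidence is in the row for the combined safety and tolerability objective.

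SAP 9.3 gives the whole derivation: "Number and percentage of patients discontinued study treatment due to tolerability will be summarized as per recorded in the eCRF End of Treatment page". It has no definition of tolerability and no link to the adverse event page.

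SAP 5.1 shows what the End of Treatment page offers: "Primary reasons for treatment discontinuation collected on the eCRF will be summarized with the following categories separately". Nine categories follow. One is adverse event. Another is "Treatment Discontinuation due to Tolerability Issues". Physician decision, withdrawal by patient and other are also on the list.

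Protocol 7.1.1 allows one reason per patient: "In case of more than one reason, the main one will be reported in eCRF". The same section introduces its list with "Patients with tolerability issues, or worsening of symptoms and/or signs may be discontinued at any time during the study for the following reasons". Six reasons follow, with adverse events first and no tolerability item.

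Separately, SAP 9.1.7 says that TEAEs with action taken *Drug Withdrawn* "will be considered as TEAEs leading to treatment discontinuation and will be summarized by SOC and PT". SAP 9.1.1 adds a summary row for ocular TEAEs that lead to treatment discontinuation.

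**The concern.** The two categories overlap by the documents' own definitions. Any unfavourable and unintended symptom is an adverse event, so eye pain that makes a patient stop the drops is both an adverse event and a tolerability problem. With one reason allowed and no coding rule in either document, the investigator has to pick. Protocol 7.1.1 treats tolerability as the general condition and adverse events as the first specific reason beneath it, so picking adverse event would be reasonable. A patient recorded that way does not enter the SAP 9.3 count.

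Better tolerability is the stated motive for the new concentrations. Protocol 6.2 cites eye pain in 42% to 63.5% of patients in earlier dry eye studies. Under Protocol 10.6.2, if both concentrations beat vehicle, the choice between them rests partly on safety data. A tolerability rate that depends on coding habits is a weak input to that choice. For these patients the error can only lower the count.

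**Working it through.** The plan states no expected rate, power or sample size for this endpoint, so there is no figure to reproduce. The check is a trace through the text, followed by an illustration of scale.

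**Trace for one patient who stops because of drug-related eye pain**

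| Recorded as | Counted in SAP 9.3? | In SAP 9.1.1 and 9.1.7 tables? |
|---|---|---|
| Tolerability issues | Yes | Yes, if the event's action is *Drug Withdrawn* |
| Adverse event | No | Yes, if the event's action is *Drug Withdrawn* |
| Physician decision or withdrawal by patient | No | Yes, if the event's action is *Drug Withdrawn* |

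The right-hand column does not depend on the End of Treatment reason. The middle column depends on nothing else.

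**Scale (assumptions, not document figures)**

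Let p be the true share of an arm stopping for drug-related ocular intolerance, and f the share of those recorded under adverse event. Then

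counted rate = p × (1 − f).

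With 97 patients per arm (Protocol 10.1), the true numbers are 97 × 0.05 = 4.85, 97 × 0.10 = 9.7 and 97 × 0.15 = 14.55. The counted rates are:

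| p | f = 0 | f = 25% | f = 50% | f = 75% | f = 100% |
|---|---|---|---|---|---|
| 5% | 5% | 3.75% | 2.5% | 1.25% | 0% |
| 10% | 10% | 7.5% | 5% | 2.5% | 0% |
| 15% | 15% | 11.25% | 7.5% | 3.75% | 0% |

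**Comparison between arms**

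If f is the same in both arms, the counted difference is (p_active − p_vehicle) × (1 − f). The absolute difference shrinks by the factor 1 − f, while the ratio of the two rates is unchanged. This needs no difference in coding between arms.

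**Can the existing tables be combined?**

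Let A be the patients counted in SAP 9.3 and B those in the ocular row of SAP 9.1.1. The number in either group is A + B − (A and B). The tables give A and B but not the overlap, so they place the total only between the larger of A and B and the sum A + B. B also includes ocular events unrelated to study drug, because that row has no causality restriction.

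**The case against.** The strongest reply is that nothing disappears from the report. SAP 9.1.1 already gives, by arm, the number and percentage of patients with an ocular TEAE leading to treatment discontinuation. SAP 9.1.7 adds tables by organ class and term and a by-patient listing, all independent of the End of Treatment reason. SAP 5.1 shows both reason categories by treatment group. TEAE incidence also serves tolerability, and safety data are not formally tested (SAP section 9). All of this stands, and it limits the point to one descriptive endpoint. It does not close the gap: those tables do not feed SAP 9.3, and as shown above they cannot be added to it. A reader could match patients by hand from listings, but only after the fact and under a rule chosen then.

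Three stronger readings are tempting and are not supported:

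- A reader might infer that patients who stop for eye pain *are* left out. The documents show only that they may be. The eCRF page and its completion guidelines are not available, and a form with its own tolerability category may lead some sites to use it for such stops. The list in Protocol 7.1.1 differs from the eCRF list and does not show how sites code.
- A reader might infer a large undercount from the 42% to 63.5% eye-pain figures. Those are incidences of eye pain, not of stopping treatment, and they say nothing about f.
- A reader might infer that coding differs between arms. Investigators are masked and nothing shows this. More patients would be missed in an active arm only if more patients there stop for this reason.

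A further fair objection concerns the remedy. Counting every ocular TEAE with drug withdrawn would treat stops for unrelated events, such as an infection or injury, as intolerance. The added definition should therefore be limited to drug-related events.

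**Conclusion.** The point holds as a weakness of definition. SAP 9.3 makes the only endpoint tied to the stand-alone tolerability objective depend on which of two overlapping categories an investigator selects. The undercount of patients stopping for drug-related ocular events is unknown and can range from none to all of them; at an assumed true rate of 10%, the reported rate could lie between 10% and 0%.

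This rests on reading the End of Treatment page as single-choice, which follows from the words about primary and main reasons in SAP 5.1 and Protocol 7.1.1, since the form itself cannot be seen. It also rests on there being no coding rule outside the two documents. No alpha, power or efficacy conclusion is affected. The change is worth making because it is cheap and removes most of the dependence on coding.

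**What to change.** Before unmasking, add to SAP 9.3 a second, de-duplicated count by arm in the safety population. A patient is counted once if either condition is met:

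- the End of Treatment reason is tolerability issues; or
- the patient has an ocular TEAE related to study drug (possible, probable or highly probable, as in SAP 9.1.2) with action taken *Drug Withdrawn*.

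Give the number, the percentage and a two-sided 95% confidence interval. Clopper-Pearson would match the method the SAP already uses for a proportion in 8.2.1.1. Show the eCRF-only count beside it, so that the effect of coding is visible. State that a missing relationship is handled as in SAP 9.1.2, where it counts as related.

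All variables are already collected, so the cost is a small extra derivation and one more table row. The reported rate may be less favourable than the eCRF-only figure. One limit remains: a patient who stops for intolerance with neither the tolerability reason nor a related ocular event marked as leading to withdrawal would still be missed.

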9.4. Ophthalmological assessments

Relevant ophthalmological examinations will be performed at indicated visits in the Schedule of Activities ([Appendix 13.1](#)). Summary of ophthalmological examinations will be based on the SAF and summarized by Eye.

9.4.1. Slit Lamp Biomicroscopy

CCI [REDACTED]

A by-patient listing will also be provided by site.

9.4.2. Specular Microscopy

Specular microscopy will be performed to assess corneal endothelial cells density (cells/mm²) at selected sites that have a specular microscope already available.

Results will be summarized using descriptive statistics at each scheduled visit for both eyes (Study Eye and fellow). Mean change from baseline at each post-baseline visit will also be summarized.

A by-patient listing will be provided by site.

9.4.3. Dilated Fundus Exam

Dilated fundus exam includes evaluation of vitreous, retina and optic nerve for vitritis, vitreal or retinal hemorrhage, maculopathy, retinal tears or detachment, posterior vitreous detachment, optic nerve appearance, and optic nerve cup-to-disc ratio. CCI [REDACTED]

The results of dilated fundus examination will be summarized using descriptive statistics at each visit for both eyes (Study Eye and Fellow Eye). Numbers and proportions of patients with vitritis, retinal or vitreal hemorrhages, retinal or posterior vitreal detachment, retinal tears, or maculopathy will be summarized at each visit. Shift from baseline of proportions will also be summarized for each parameter. Actual observed values and change from baseline at each post-baseline visit will be summarized for cup-to-disc ratio.

A by-patient listing will be provided by site.

9.4.4. Bulbar Conjunctival Redness

Bulbar conjunctival redness will be assessed at the slit-lamp using white light prior to vital dye instillation and graded according to the Validate Bulbar Redness (VBR 10) scale that has 10 reference images with increasing bulbar redness. The scale starts at grade 10 and has 10-point steps between reference images (score range 10-100). CCI [REDACTED]

The results of bulbar conjunctival redness score will be summarized by conjunctiva (nasal and temporal) using descriptive statistics at each scheduled visit and applicable time point for both eyes (Study Eye and Fellow Eye). Mean change from baseline at each post-baseline visit will be summarized.

A by-patient listing will be provided for both eyes by site.

9.4.5. External Ocular Examination

External ocular examination will be performed on both eyes at Screening, Baseline, Week4 and Week8 or at the Early Termination Visit.

A by-patient listing will be provided for both eyes by site.

10. Interim Analysis

No interim analyses are foreseen.

11. Changes in the Planned Analysis

The Mean change from baseline in total CCI [REDACTED] in the Study Eye at week 8 will be considered a secondary endpoint CCI [REDACTED]. This was a typo in the protocol.

12. References

OXERVATE™ US package insert. Boston, MA: Dompe' U.S. Inc; 2018

Hochberg Y. A sharper Bonferroni procedure for multiple tests of significance. Biometrika 1988;75:800-2.

Permutt T and Feng L. Trimmed means for symptom trials with dropouts. Pharmaceuticals Statistics. 2017;16:20-28.

13. Appendices

13.1. Schedule of Activities

	Run-In period		Treatment period		Follow-up period
	V1 Screening (Day -12)	V2 Baseline (Day 1)	V3 Week 2 (Day 13)	V4 Week 4 (EOT) (Days 28)*	V5 Week 8 (EOS) (Days 56)*
Interval Tolerance (days)	±2		±1	±1	±2
Site Visit	X	X	X	X	X
ELIGIBILITY					
Informed consent	X				
Inclusion / Exclusion criteria	X	X			
Demographics, Medical History, Medications	X				
TRIAL INTERVENTIONS					
Randomization		X			
Trial Study Product dispensation**	X	X	X		
Artificial tears dispensation				X	
Patient Instruction	X	X		X	
Application of CCI by the investigator	X				
Patient's Diary dispensation	X	X		X	
Documentation in patient's medical record of first dose administration by Investigator	X				
Medication dosing compliance verification (diaries)		X	X	X	X

TRIAL PROCEDURES					
Check the Patient Diary		X	X	X	X
SANDE questionnaire	X	X		X	X
CCI [REDACTED]	CCI [REDACTED]				
BCDVA by ETDRS	X	X		X	X
External Ocular Examination	X	X		X	X
CCI [REDACTED]	CCI [REDACTED]				
Schirmer-I test without anesthesia	X	X		X	X
Slit Lamp Examination	X	X		X	X
Redness score (VBR 10)	X	X		X	X
Instill fluorescein	X	X		X	X
fTBUT	X	X		X	X
CCI [REDACTED]	CCI [REDACTED]				
CCI [REDACTED]	CCI [REDACTED]				
Conjunctival lissamine green Staining NEI scale.	X	X		X	X
CCI [REDACTED] before and after CCI [REDACTED] ***	CCI [REDACTED]				
Specular microscopy (Corneal endothelial cell density) (in selected centers)		X			X
Instill tropicamide CCI [REDACTED]		X			X
Dilated fundus examination		X			X
Collect used/unused Study Product (to be checked by independent personnel)		X	X	X	

Retrieve Patient Diary		X		X	X
Concomitant medications****		X	X	X	X
Adverse events evaluation		X	X	X	X
LABORATORY TESTS					
Pregnancy Test	X	X		X	

*In case of premature discontinuation of the study, the patient will be required to participate at the Early Exit Visit that will have the same assessment of Visit 4 (in case of early treatment discontinuation before Visit 4) or the same assessment of Visit 5 (in case the discontinuation from the study will occur after the ending of the treatment but before the expected Visit 5). A flag will be inserted in the eCRF to define if the Visit 4 or 5 is a per protocol visit or if it is done as Early Exit Visit.

** An CCI kit will be also provided

^ CCI will be administered to all subjects but completed only by those that either have CCI or have filled this form before.

*** Only in patients with CCI >0

**** All ocular and systemic medications, over-the-counter painkillers, herbal products, vitamins, and antacids taken within 4 weeks prior to the start of and throughout the study will be clearly documented on the Concomitant Medications eCRF page.

